2.5.3 Allocation to treatment

Intra-patient randomization and allocation of treatment is planned. Wounds will be matched according to wound characteristics e.g. size, severity, and location. Randomization will be computer generated.

2.5.4 Unblinding

Clinical study is not blinded.

2.5.5 Treatment/matrix adherence

Treatment will be applied by investigator (initial application and reapplication on Day 0). Subsequent treatment will be applied by caregiver during the scheduled visit for Week 1, Week 2, Months 1, 2 and 3 if needed. More frequent application to the treatment wounds is allowed (up to once a week).

2.5.6 Withdrawal of subjects due to non-compliance

Subjects are allowed to withdraw at any time during the entire study period. They should contact the PI directly and attend an early study termination clinic visit to assess for adverse events and discuss ongoing treatment.

Subjects may withdraw from study participation due to non-compliance or patients may choose to discontinue. Recruitment of subjects will continue until the minimum number of wounds is met (20 treated and 20 control wounds).

2.5.7 Procedures to assess efficacy

Wounds will be assessed by investigator review of photographs for achievement of >90% healing from baseline every two weeks for a total of 16 weeks (4 months). Wound photos will be captured every two weeks by the subject or caregiving using mobile phone photographs uploaded into REDCap. Patient reported pain and itch surveys (Wong-Baker FACES scale and Itch Severity Scale (adults) / Itchy Man scale (minors) will be analyzed.

The aim is to analyze all data using an intention to treat analysis method. Further sub-analysis will be undertaken e.g. analyze data from patients who have applied the Spincare matrix 80% of the expected number of times or greater.

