2.3.1 General study design

Pilot study in 6-10 subjects where wounds will be randomized 1:1 to matrix or no treatment (control): Patients will be asked to review and sign the informed consent form. The matrix will be applied to randomized treatment wounds (computer generated randomization), along with a non-adhesive bandage as a protective layer. At the time of matrix application, the investigator will score amount of wound burning, pain, or other adverse events. Non-treated wounds will have the patient's standard of care, and the non-adhesive bandage applied. Reapplication of matrix treatment may be required soon after the initial application depending on how well the matrix has propagated with the first application. Subjects and caregivers will be trained on how to take photos. We will ensure that photos of the face are NOT included to protect patients' confidentiality. One day after a wound examination will be performed in clinic. The investigator will assess the adherence of the matrix, and any adverse events (AEs).

Thereafter a caregiver may travel to the participants home to apply the matrix device to randomized, treated wounds once a month or more frequently if required (up to once-a-week application is allowed, the patient will record when they have applied the matrix treatment at home and the reason). Spray application(s) may be skipped at the discretion of the PI to address any concerns or adverse events. Investigators will perform remote monitoring (via phone call or virtual platform) at Week 1, Week 2, Month 1, Month 2, Month 3 and Month 4 (additional interim visits may be required) to assess for adverse events and track progress. Additional photographs will be taken, and investigators will use Telehealth to monitor for healing and safety reporting. Compliance is verified by bi-weekly photographs. Wound swabs of treated and untreated wounds will be taken prior to spray treatment and at Month 2 and Month 4. After Month 1, patients are given the option to not put any dressings on their wounds if this is medically acceptable and in line with the patient preference. Throughout the visit wound closure assessments may not be always possible if the Spincare matrix is still intact and this will be indicated on the source document. No Spincare treatment is to be applied 2 weeks prior to the end of the visit to allow for wound size measurement.

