Week 1, Week 2, and Months 1, 2, 3, 4 – Investigators will arrange telehealth assessment at Week 1, Week 2, Month 1, Month 2, Month 3 and Month 4 (additional interim phone call visits/telehealth assessment at **Week 6, Week 10 and Week 14**, or more frequently, if deemed necessary). A caregiver may travel to the participants home to apply the matrix device to randomized, treated wounds (up to once a week if needed, they will record the date of application and the reason). Additional photographs will be taken, and investigators will use Telehealth to monitor for healing and safety reporting. At the time of matrix application, the caregiver will score amount of wound burning, pain, or other adverse events. Matrix will not be applied after **Week 14** to ensure the final wound assessment at Month 4.

Month 4 – Telehealth (End of Randomized Phase) Visit: The investigator will virtually assess wound healing compared to baseline photographs in the treated and control wounds. Digital photographs of the treatment and control wounds will be taken with a ruler by the caregiver/participant and sent to the investigator. All wound photos will be stored and reviewed on the REDCap. The participant's preference to enroll on the Open-Label Phase will be assessed.

Open-Label Phase:

Participants who are eligible for the Open-Label Phase, at the discretion of the investigators (taking into consideration participant's prior documented adverse events, current medical status, and adherence to trial protocol), and who choose to participate, will be provided with the Spincare matrix and will be instructed to apply it once a week at most. Participant will be allowed to treat previously randomized wounds (treated and control wounds) and new wounds, up to a max of 10 individual wounds; there won't be control nor randomized wounds. The wounds would be selected at the Open-Label Baseline remote visit and will need to meet the same wound criteria as the Randomized phase. At minimum during each monthly visit, participants will be required to provide digital photos taken with a ruler before and after the application of the Spincare matrix. Additionally, they will complete surveys regarding their pain and itch, offer updates on their

medical history, provide information about concurrent medications, and report any adverse events. No blood draws, wound cultures and in person visits will be required during the Open-Label phase.

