5.0 MONITORING PROCEDURES

Monitoring of the study for compliance with the clinical protocol will be conducted every 4 months or when the first subject completes the trial. Monitoring will be done by a qualified staff of Stanford (e.g. Stanford Dermatology Project Manager of clinical trials with [name], EB investigator not affiliated with this study). [name] will also review the wound healing and AE results after the first 2 adult subjects complete the trial before any pediatric subjects will be enrolled.

The sponsor-investigator will permit direct access of the study monitors and appropriate regulatory authorities to the study data and to the corresponding source data and documents to verify the accuracy of this data.

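### The >90% closure calls behind the primary endpoint are read from photographs without masking, although coded, random-order reading by an existing investigator is practicable

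*Combined protocol and SAP*

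**What the plan says.** Section 2.5.7 sets the efficacy read: "Wounds will be assessed by investigator review of photographs for achievement of >90% healing from baseline every two weeks", over 16 weeks, from mobile-phone pictures uploaded by the patient or caregiver. The primary endpoint in Section 2.6.1 is the duration of wound closure in weeks, matrix against control, from baseline to Month 4.

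Four other places show who reads the images and what that person knows:

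- Section 2.5.4: "Clinical study is not blinded".
- Section 2.5.5: "Treatment will be applied by investigator (initial application and reapplication on Day 0".
- Section 2.5.2, Month 4 visit: "The investigator will virtually assess wound healing compared to baseline photographs in the treated and control wounds".
- Section 2.5.2, same visit: "All wound photos will be stored and reviewed on the REDCap".

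Two further statements bear on how far a read can be masked. Section 2.3.1 notes that "wound closure assessments may not be always possible if the Spincare matrix is still intact". Section 2.5.2 stops application after Week 14 "to ensure the final wound assessment at Month 4".

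No section describes a masked reader, a coded image set, a second reader or adjudication.

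**The concern.** Whether a wound has passed 90% closure on a home photograph is partly a judgement. Here it is made by people who can know which wound was treated, and who state in Section 2.6.3 that they expect more matrix wounds to reach the threshold. Randomization is within patient between matched wounds (Section 2.5.3), so the reader contrasts a known treated wound with a known control in the same person.

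Reads fall on a 2-week grid. A borderline wound called closed one visit early therefore moves by a full 2 weeks. If such calls lean one way in one arm, the lean enters the treatment difference directly, and neither randomization nor the planned intention-to-treat analysis removes it. The protocol intends the results to guide the design of larger studies, so a reader-dependent effect could be carried forward.

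The device cannot be masked from patient or caregiver. The photograph read is a separate step, and it can be masked at least in part.

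**Working it through.** **1. Is the read masked?** This is a question of text. Section 2.5.7 gives the call to the investigator. Section 2.5.4 says there is no blinding. Section 2.5.5 has the investigator apply the matrix, and Section 2.5.2 has the investigator compare treated with control wounds at Month 4. Nothing elsewhere separates the reader from the allocation, so the closure calls are unmasked.

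**2. Does the primary endpoint depend on these calls?** Section 2.6.1 does not repeat the >90% threshold or say how biweekly calls become a duration. Section 2.5.7 and the synopsis row on efficacy evaluations give >90% closure as the efficacy criterion, and no other basis for the duration is described. The dependence is an inference, but no other source is offered.

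**3. Number of reads.** 16 weeks / 2 = 8 reads per wound. At the planned minimum of 40 wounds, 40 × 8 = 320 follow-up images, plus 40 baseline images.

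**4. The plan's own figure.** Section 2.6.2 states 90% power for 20 against 20 wounds, 8.5 against 6 weeks, SD 3, two-sided alpha 0.05.

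- SE = 3 × √(2/20) = 0.949 weeks.
- Power = Φ(2.5/0.949 − 1.96) = Φ(0.675) = 75.0% (72.8% with the t distribution).
- A paired t-test on 20 pairs comes to about 90% (89.7%) if a within-pair correlation of 0.4 is assumed. The plan states none.

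The 90% is therefore not reproduced as two independent groups. That is a separate matter, and masking the reader does not change it. Only the SE and the 2.5-week target are used below.

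**5. Illustration of size.** Assumption, not from the documents: a share p of matrix wounds is called closed exactly one visit early, control wounds are read correctly, and the SD is unchanged. The bias is b = 2 × p weeks. With no true effect, the two-sided rejection rate (unpaired, normal) is 1 − Φ(1.96 − b/SE) + Φ(−1.96 − b/SE).

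| Assumed share p | Bias b (weeks) | b / 2.5 | b / SE | Rejection rate, nominal 5% |
|---|---|---|---|---|
| 10% | 0.2 | 8% | 0.21 | 5.5% |
| 25% | 0.5 | 20% | 0.53 | 8.2% |
| 50% | 1.0 | 40% | 1.05 | 18.4% |

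With a paired t-test on 20 pairs and an assumed within-pair correlation of 0.5, the rates are 5.9%, 10.9% and 29.4%.

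**6. Direction.** The synopsis speaks of a 2.5-week longer closure and Section 2.6.2 of a 2.5-week shorter one. An early call on a matrix wound favours matrix either way: it shortens time to closure, or lengthens time spent closed if the wound stays closed.

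**7. Which images matter?** A Month 4 read gives closed or not closed at one time point. It cannot show that a wound was called closed at Week 6 rather than Week 8. The masked read must therefore cover all biweekly images.

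**The case against.** The strongest reply is that this is a declared open, single-site feasibility pilot looking for early signals, and that the reads are not free judgement. Month 4 photographs include a ruler, and the Section 2.5.9 schedule has wound size measured on Day 0, Day 1, Week 1 and Months 1 to 4. This reduces subjectivity but does not remove it. The same table marks home photographs but no size measurement at Weeks 6, 10 and 14, and nothing says that size is measured without knowledge of the allocation.

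A second reply is that masking would be imperfect and not free. That stands. Investigators inspect matrix adherence on Day 1 and follow the wounds by telehealth, so any of them may recognise a wound. Matrix can appear only on treated wounds, so an image that shows it reveals the allocation. Setting such images aside would lose data from one arm only. Cropping, coding and ordering some 320 images is work, and the documents do not say that REDCap can hide the allocation.

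A third reply is that the shares of 10%, 25% and 50% are invented. They are, and at the lowest share the effect on the error rate is small. Also, the 2-week step applies to one wound while the 2.5-week target is a difference in means, so the two are not directly comparable.

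A reader might also infer three things that the documents do not support:

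- That Month 4 images will be free of matrix. The plan stops application about two weeks earlier, but gives no time for the matrix to detach or degrade.
- That the "EB investigator not affiliated with this study" in Section 5.0 is available as reader. That person has a monitoring role, and the healing review described covers the first two adults before pediatric enrolment. No image reading is assigned.
- That a masked Month 4 read would test the primary result. It supports closure status only.

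**Conclusion.** The point holds. The >90% calls that feed the duration endpoint are made by investigators who know, or can know, which wound was treated, and the plan does not mask the read. This is an avoidable risk of bias in the primary comparison. It is not evidence that the result will be biased, and an open design is not in itself an error in a pilot of a visible device.

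The documents cannot give the size. On the assumed one-arm shares, the shift is 0.2 to 1.0 week, or 8% to 40% of the 2.5-week target. This rests on one-visit errors, correct reading of controls and an unchanged SD.

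The change should be made. It needs no new reader and no change for patients, and it reduces the risk without removing it.

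**What to change.** Amend Section 2.5.7 as follows:

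- Crop the photographs already held in REDCap to the wound, code them, and present them in random order within patient with the allocation hidden. Give each with the coded baseline image of the same wound, because the threshold is relative to baseline. Someone other than the reader should prepare the set.
- Have >90% closure called by an existing study investigator, preferably the one least involved in applying and following the matrix.
- Apply this to every biweekly image and use these calls for the primary endpoint.
- Have the reader record whether matrix is visible. Keep those images in the primary analysis, and report a sensitivity analysis by visible matrix. State in advance how a read is handled when matrix prevents a call.
- Report the masked Month 4 read as support for closure status only.

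The cost is preparing about 320 follow-up images plus baselines, and a reading view without the allocation, which must be confirmed as feasible in REDCap. Masking will be incomplete where matrix shows or the reader recognises a wound, and the report should say so. Visits, treatment and patient procedures stay as they are.

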2.5.2 Study treatment or diagnostic product procedures

The Spincare device produces a wound dressing matrix that is sprayed to the wound bed. It uses a laser system to help with correct distance position to produce a uniform matrix that is electrospun to the wound bed. The device is currently available in Israel and 11 European countries but is not FDA-approved or cleared on any indications. In the current literature the main indications are acute and chronic wounds, partial thickness burns and ulcers and the matrix treatment has been used in more than 20 countries so far. A case study of Spincare treatment in EB has been described.

A full body wound examination will be performed by the investigator and target wound areas will be identified. All eligible wound sites will be randomized for matrix treatment versus standard of care wound dressings (6 wounds, or 3 wound pairs). The matrix will be applied to randomized treatment wounds, along with a non-adhesive bandage (e.g. Telfa, Mepitel, Rylon, etc.) as a protective layer. At the time of matrix application, the investigator will ask about any potential wound burning sensations, pain, or other adverse events. Non-treated wounds will have the patient's standard of care and non-adhesive bandage applied. Subjects and caregivers will be trained on how to take photos. Wound pain and itch are captured at least every 2 weeks.

The matrix treatment will be applied on Day 0 in clinic. Day 1 visit will be mandatory to assess for any adverse events (Day 2 is optional and may be required particularly if AEs have occurred and this will be at the discretion of the

PI). Subsequent applications will be performed by a caregiver if needed up to once a week.

Detailed Schedule:

Randomized phase:

Day 0 – Spincare would be applied to wounds after randomization process and covered with a non-adhesive dressing. Reapplication of matrix treatment may be required depending on how well the matrix has adhered with the first application. The need for this will be assessed by the investigators.

Day 1 – A wound examination will be performed in clinic one day after the initial application. The investigator will assess the adherence of the matrix, and any adverse events (AEs).

Day 2 is optional and may be required if medically indicated at the discretion of the PI.

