2.5.9 Schedule of study visits

	Randomized Phase												Open-Label Phase				
	Day 0	Day 1	Week 1	Week 2	Month 1	Week 6	Month 2	Week 10	Month 3	Week 14	Month 4 ^a	Baseline ^b	Month 1	Month 2	Month 3	Month 4	
	Clinic Visit		Phone Call										Phone Call				
Medical History	X	X	X	X	X		X		X		X	X	X	X	X	X	
Adverse Events		X	X	X	X		X		X		X	X	X	X	X	X	
Vital Signs	X	X															
Direct Skin examination	X	X															
IGA grading			X		X		X		X		X	X	X	X	X	X	
Wound selection and randomization	X												X ^c				
Application of matrix in clinic	X	X															
Application of matrix at home			X	X	X	X	X	X	X			X	X	X	X	X	
Wound culture	X						X				X						
Itch and pain scores	X		X	X	X	X	X	X	X	X	X	X	X	X	X	X	
Caregiver survey									X		X						
Wound size measurements	X	X	X		X		X		X		X	X	X	X	X	X	
Photographs by investigator	X	X															
Photographs at home			X		X	X	X	X	X	X	X	X	X	X	X	X	

Study timeline:

Randomized Phase:

Day 0: in person visit; randomization of wounds with wound photography, application of matrix and monitoring of adverse events (matrix application within 30 days of screening).

Day 1: in person assessment of wounds.

Day 2 (optional): review of wounds with photographs.

Telehealth assessment at **Week 1, Week 2, Month 1, Month 2, Month 3 and Month 4** (a window of ± 7 days for the monthly scheduled visits is expected).

Participant will provide pain and itch surveys and photographs every two weeks.

Additional visits (over secure video platform or phone calls), and reapplication of matrix by caregiver may be scheduled if deemed necessary.

Open-Label Phase:

Baseline Open-Label: telehealth assessment; selection of wounds and baseline wound photography, application of matrix and monitoring of adverse events.

Telehealth assessment at **Open-Label Month 1, Open-Label Month 2, Open Label Month 3 and Open-Label Month 4** (a window of ± 7 days for the monthly scheduled visits is expected). Participant will provide pain and itch surveys and photographs at every Open-Label Month visit. Participants can reapply up to once a week. Additional visits (over secure video platform or phone calls), and reapplication of matrix by caregiver may be scheduled if deemed necessary.

a The **Baseline Open-Label** visit could be done during the **Randomized Phase Month 4**.

b The **Baseline Open-Label** visit could be done up to two weeks after the **Randomized Phase Month 4** visit.

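### Does the 80%-of-expected-applications sub-analysis need a defined expected number, given that the matrix is applied as needed?

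*Combined protocol and SAP*

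**What the plan says.** Section 2.5.7 sets intention to treat as the aim for all data. It then mentions further sub-analysis and gives one example: to "analyze data from patients who have applied the Spincare matrix 80% of the expected number of times or greater". Section 3.3 repeats intention to treat for patients withdrawn because of adverse effects.

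The expected number is not given anywhere. The sections on application read as follows:

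- Section 2.3.1: "once a month or more frequently if required (up to once-a-week application is allowed". It also says "Spray application(s) may be skipped at the discretion of the PI to address any concerns or adverse events".
- Section 2.5.2: "Subsequent applications will be performed by a caregiver if needed up to once a week". For home treatment it adds "randomized, treated wounds (up to once a week if needed, they will record the date of application and the reason". Application ends at Week 14 "to ensure the final wound assessment at Month 4".
- Section 2.5.5, on adherence: "Subsequent treatment will be applied by caregiver during the scheduled visit for Week 1, Week 2, Months 1, 2 and 3 if needed".
- Section 2.5.9: the row "Application of matrix at home" has seven marks in the randomized phase.

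Section 2.5.3 randomizes wounds within patients and section 2.4.3 requires at least three pairs per patient, whereas the 80% rule selects patients.

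**The concern.** A percentage needs a denominator, and the text can be read as giving four: about 3 home applications (monthly), 5 (the listed visits), 7 (the schedule table) or 14 (the weekly maximum up to Week 14). The same patient can be in the subset on one reading and out on another. In an open-label study this small, such a choice made after seeing the data is unattractive.

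There is also a possible selection effect. Patients enter or leave whole, so both wounds of a pair go together, but the count comes from the treated wounds alone. If the expected number is fixed and application stops once a wound has closed, a fast-healing treated wound lowers the patient's count. The subset would then favour slow treated wounds and the comparison would move against the matrix. Section 2.6.3 wants the results to inform later studies, so a distorted adherence result could mislead.

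**Working it through.** The plan gives no figure to reproduce here, so the check asks how much depends on the missing definition.

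**1. Thresholds.** With E expected home applications, the requirement is 0.8 × E rounded up: 2.4 → 3, 4.0 → 4, 5.6 → 6, 11.2 → 12, for E = 3, 5, 7 and 14. A patient treated at all five visits of section 2.5.5 scores 5/3 = 167%, 5/5 = 100%, 5/7 = 71% or 5/14 = 36%. The ambiguity is real.

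**2. Early closure under a fixed number.** Assume application stops at closure. A treated wound closing at 6 weeks, the matrix planning value in section 2.6.2, has had 1/3 = 33%, 3/5 = 60%, 4/7 = 57% or 6/14 = 43% of the expected applications. All are below 80%.

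**3. Size of the shift.** The simulation used 200,000 patients per setting, three pairs each, and time to closure Normal(8.5, 3) in both arms, so there is no true effect. The 8.5 and the SD of 3 come from section 2.6.2. Assumed: a within-patient correlation of 0.3, and a probability q that an already closed treated wound is re-treated at an occasion, standing in for re-blistering. Entries are treated minus control, in weeks; positive is against the matrix.

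| Fixed E | Any wound counts: q = 0 / 0.25 / 0.5 | Averaged over wounds: q = 0 / 0.25 / 0.5 |
|---|---|---|
| 3 | 0.98 / 0.25 / 0.07 | 1.86 / 1.16 / 0.61 |
| 5 | 0.23 / 0.04 / 0.01 | 0.96 / 0.48 / 0.18 |
| 7 | 0.55 / 0.13 / 0.01 | 1.22 / 0.79 / 0.35 |
| 14 | 0.98 / 0.26 / 0.02 | 1.84 / 1.34 / 0.68 |

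A repeat with a different random seed agreed to within about 0.02 week. At q = 0 with any-wound counting, about 29%, 86%, 60% and 29% of patients are kept. With averaging, about 5%, 36%, 24% and 7% are kept. For 7 patients (about 20 pairs at 3 each), the chance of an empty subset is (1 − share kept)^7. With averaging this is 0.945^7 = 0.67, 0.642^7 = 0.05, 0.760^7 = 0.15 and 0.931^7 = 0.61. With E = 5 and any-wound counting it is 0.14^7, about one in a million.

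The q = 0 shift depends on the correlation. Over the four schedules, any-wound counting gives 0.23 to 1.45 at correlation 0 and 0.17 to 0.57 at correlation 0.6. Averaging gives 1.83 to 3.89 and 0.45 to 0.83; the largest of these keep only 2-3% of patients.

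**4. Need-based number.** Let the denominator be the occasions when a treated wound was open. With 95% or 85% of needed applications completed, the shift lies between about −0.1 and +0.1 week on all four schedules.

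**5. Skips for intolerance.** Suppose 20% of patients get no benefit and receive half of the needed applications, and the rest gain 2.5 weeks. The effect in all patients is 0.8 × (−2.5) = −2.0 weeks. If skips count as non-adherence, the subset gives −2.4 to −2.5, close to the true effect in tolerant patients. If investigator-directed skips do not count, it gives −2.0. The first answers a different question; it is not a bias.

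**6. Which readings fit the text.** Every section on home application makes it conditional on need. Section 2.5.5 is the adherence section and lists five occasions. The table's seven marks are those five plus Weeks 6 and 10, which section 2.5.2 treats as interim contacts held if necessary. Fourteen follows from a maximum, which is not an expectation. The monthly wording is open-ended. These look largely like scheduled, optional and maximum occasions within one as-needed regimen. This concerns the analysis denominator only; no view is taken on how often the matrix should be applied.

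**The case for a change.** The strongest case for a change is textual. The plan commits to sub-analysis, its only example rests on an undefined quantity, and the choice decides who is analysed in an unblinded study. A definition would cost a sentence or two. Under a fixed count averaged over wounds, the shift can approach the planned difference, or exceed it if wounds are uncorrelated, and the subset may well be empty.

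The missing definition and the missing wound-to-patient rule stand as facts. The size of the harm does not. The large figures need a fixed number, averaging over wounds and little or no re-treatment; the 61-67% chance of an empty subset also needs the monthly or weekly denominator. Counting how many times a patient applied the matrix reads most simply as occasions per patient. No re-treatment is a poor assumption when the synopsis describes wounds that heal and re-blister, and section 2.6.2 expects most pediatric wounds to be of that type. Replacing the subset with a purely descriptive report is a choice on which statisticians reasonably differ.

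**Conclusion.** No change follows. The expected number is undefined, but it belongs to one illustrative sub-analysis beside an intention-to-treat analysis that it cannot affect. An analyst would fill the gap sensibly by counting an application as expected when it was needed and had not been withheld by the investigator; application dates and reasons are already recorded. On that reading the shift is within about 0.1 week. On the five listed visits with any-wound counting it is about 0.2 week without re-treatment and at most 0.04 week with it, against a planned difference of 2.5 weeks.

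These sizes assume a within-patient correlation of 0.3, normally distributed closure times, and the endpoint read as time to closure, as in section 2.6.2. The synopsis describes the benefit in the opposite direction, as longer closure, so the direction and size in weeks are illustrative. The conclusion does not rest on them: without a fixed denominator and application that stops at closure, neither of which the plan states, this selection effect does not arise.
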